2.3 Benefit/risk assessment

Overall, the AE profile of PSL in clinical pharmacology studies is consistent with the pharmacological activity of the product, and, as expected, in the context of early dose escalation studies in healthy study participants. The safety findings to date suggest that the AEs experienced by study participants receiving single and repeated doses of PSL are limited principally to CNS effects. The AEs tend to be dose related in frequency and intensity, self-limiting, and tend to decrease in intensity over the first few days of dosing.

As described in the Investigator's Brochure, the overall safety for the Phase 1 studies was generally good at doses up to 400mg BID administration. As of the cut-off date of 06 Dec 2019, there have been 2 serious adverse events (delirium and mania) and no deaths during the studies. Of the treatment emergent adverse events (TEAEs) occurring in 247 healthy study participants and 79 study participants with epilepsy exposed to PSL, 3 study participants reported 47 severe TEAEs, with the most prevalent being somnolence, fatigue and balance disorder. The severe psychiatric AEs that have occurred in Phase 1 and Phase 2 studies were delirium, depressed mood, and insomnia. These severe psychiatric adverse events were transient, and the symptoms resolved after withdrawal of PSL. The possibility of acute psychiatric AEs highlights the need to maintain vigilance for such effects and to monitor for any psychiatric/mood/behavioral signs in studies with healthy study participants and in studies with epilepsy patients.

Acute psychiatric events of transiently severe intensity were observed in 2 healthy study participants in UP0035. Such events are considered to be part of the identified risks of acute psychiatric incidents per the Safety Risk Management Strategy; ie, it is not unexpected for this type of event to occur, especially with repeated dosing at 400mg BID. The Safety Risk Management Strategy already considers that:

- Psychiatric and behavioral symptoms may require dose reduction or discontinuation.
- Study participants should be withdrawn if they develop psychiatric/mood/behavioral signs or disturbances that are ‘clinically concerning’ or that worsen over time.
- Clinically significant psychiatric AEs will lead to prompt withdrawal from studies.

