## 2 PROTOCOL SUMMARY

### 2.1 Study objectives and endpoints

**Table 2-1: Objectives and endpoints**

Objectives	Endpoints
Primary	

 
• To investigate the effect of steady-state PSL (400 mg twice daily (BID) or 200 mg BID) on the pharmacokinetics (PK) of a single dose oral contraceptive containing EE 30µg and LN 150µg.
 
	
 
– Cmax and AUC of EE and LN
 

Secondary	

 
• To evaluate the safety and tolerability of PSL in healthy female study participants.
 
	
 
– Incidence of TEAEs and SAEs
 

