### 3.6 Treatment assignment

It is expected that study participants will receive treatments as per the randomized treatment sequence and hence the analyses will be based on the randomized treatment. If a study participant was randomized but not dosed in any treatment period, the study participant results will be reported under the randomized treatment group. For safety analyses based on the SS, study participants will be classified according to the medication that was actually received.

Except for PK, concomitant medications, and adverse events, tables will be presented separately for each study part by randomized Treatment Sequence (Sequence A: PSL+ OC followed by OC alone and Sequence B: OC alone followed by PSL+OC) and overall. Listings will be presented by study part, randomized treatment sequence, and study participant number. PK summaries will be presented by study part, treatment period (OC alone and OC+PSL), and analyte (EE, LN; PSL and its metabolites). Concomitant medication and adverse event tables will be presented separately for each study part by treatment (OC alone, PSL alone, and OC+PSL).

A detailed schematic diagram of the study is provided in [Table 2-2](#) and [Table 2-3](#).

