### 3.9 Changes to protocol-defined analyses

- Changes in the name of analysis datasets (section 9.1 of the protocol):
  - The analysis set “Enrolled set” will be renamed as “All Study Participants” in the SAP and will correspond to all study participants who sign the informed consent form.
  - The analysis set “Pharmacokinetic Per Protocol Set (PK-PPS)” will be renamed as “Pharmacokinetic Set (PK Set)” in the SAP and will still correspond to the protocol definition of PK-PPS.
- For the purpose of the analysis of concomitant medications and adverse events 3 groups will be created, based on the treatment administered. The results will be presented for PSL alone, OC alone and the combination of PSL and OC.
- For the primary PK analysis, ping-pong plots have been added for EE and LN for  $C_{max}$ , and AUC for OC with and without PSL.
- Ping-pong plots have also been added for  $C_{max,ss}$  and  $AUC_{\tau}$ , for PSL and its two metabolites ( [REDACTED] and [REDACTED] ) for PSL with and without OC.
- Ping-pong plots have been added for  $C_{max,ss}$ ,  $AUC_{\tau}$ ,  $MR_{AUC_{\tau}}$ ,  $MR_{C_{max,ss}}$ ,  $CL_{ss}$ ,  $t_{1/2}$ , for PSL (with and without OC).
- Furthermore, the relationship between MR and  $C_{max}$  (with and without PSL) of EE and LN, and the exposure to PSL ( $AUC_{\tau}$ ) will be explored.
- Ctrough and MR based on  $AUC_{\tau}$  of PSL and its two metabolites, will also be compared between days (with OC [Day 13 for Sequence A and Day 30 for Sequence B] and without OC [Day 12 for Treatment Sequence A and Day 29 for Treatment Sequence B] using analysis of variance on the log-transformed parameters and estimation of geometric ratio of PK parameters between days with their 90% CI will be provided.
- Furthermore, the relationship between individual  $C_{max}$  (with and without PSL) of EE and LN and the exposure to PSL ( $AUC_{\tau}$ ) will be assessed by scatterplots and linear regression analyses.
- According to the protocol, the occurrence and incidence of AEs will be summarized by treatment sequence according to the intake of PSL (pretreatment or treatment-emergent) and

by intensity or relationship to PSL. As the relationship to PSL alone is not documented in the CRF, the relationship to study medication (PSL, PSL+OC, and OC) will be analyzed. Consequently, the definition of TEAE will be related to treatment (PSL, PSL+OC, or OC) and a TEAE will be attributed to a treatment according to the start date.

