Adverse events will be attributed to the treatment (OC, PSL or OC+PSL) after which they start. Thus, in **part 1**, for study participants randomized in Sequence A, all AEs starting after the first intake of PSL through Day 13 (prior to OC intake) will be attributed to PSL, all AEs starting after OC intake on Day 13 through Day 34 (prior to OC intake) will be attributed to PSL+OC, and all AEs starting after OC intake on Day 34 through Day 41 will be attributed to OC. In **part 1**, for study participants randomized in Sequence B, all AEs starting after the OC intake on Day 1 through Day 18 (prior to PSL intake) will be attributed to OC, all AEs starting after PSL intake on Day 18 through Day 30 (prior to OC intake) will be attributed to PSL, and all AEs starting after OC intake on Day 30 through Day 43 will be attributed to OC+PSL. In **part 2**, for study participants randomized in Sequence A, all AEs starting after the first intake of PSL through Day 9 (prior to OC intake) will be attributed to PSL, all AEs starting after OC intake on Day 9 through Day 26 (prior to OC intake) will be attributed to PSL+OC, and all AEs starting after OC intake on Day 26 through Day 33 will be attributed to OC. In **part 2**, for study participants randomized in Sequence B, all AEs starting after the OC intake on Day 1 through Day 18 (prior to PSL intake) will be attributed to OC, all AEs starting after PSL intake on Day 18 through Day 26 (prior to OC intake) will be attributed to PSL, and all AEs starting after OC intake on Day 26 through Day 35 will be attributed to OC+PSL. AEs starting more than 168 hours post last dose of study medication will be attributed to the SFU Period. A schematic summary is shown below.

Study Part	Sequence	PSL alone	PSL + OC	OC alone	SFU
1	A	Day 1 – 13 (prior to OC intake)	Day 13 (after OC intake) – 34 (prior to OC alone intake)	Day 34 (after OC intake) - 41	42+
	B	Day 18 (after PSL intake) – Day 30 (prior to OC intake)	Day 30 (after OC intake) - 43	Day 1 – 18 (prior to PSL intake)	44+
2	A	Day 1 – 9 (prior to OC intake)	Day 9 (after OC intake) – 26 (prior to OC intake)	Day 26 (after OC intake) - 33	34+
	B	Day 18 (after PSL intake) – 26 (prior to OC intake)	Day 26 (after OC intake) – 35	Day 1 – 18 (prior to PSL intake)	36+

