All AEs will be recorded in the CRF from the time of informed consent until study completion or termination. All AEs will be coded (see [Section 3.8](#)) and categorized by intensity (mild/moderate/severe) and relationship (related/not related) to study medication (PSL, PSL+OC, and OC) as judged by the Investigator.

All AE data will be listed by study part, treatment sequence, study participant number, start date, and time. The listings will include the following data pertaining to the AEs: start and end dates with relative days to study medication administration, duration, intensity, seriousness, relationship to study medication, action taken, and final outcome.

The number and percentage of study participants who experience TEAEs will be summarized by MedDRA SOC, PT, treatment sequence and treatment period.

Summaries of TEAEs will include the following:

- Overview of incidence of TEAEs (overview including number and percentage of study participants with any TEAEs, any serious AEs, TEAE of Special Interest, TEAEs leading to discontinuation, drug-related TEAEs, severe TEAEs and TEAEs leading to death; event counts will also be included)
- Incidence of TEAEs by maximum relationship
- Incidence of TEAEs by maximum intensity
- Incidence of non-serious TEAEs above reporting threshold of 5% of study participants

Summary tables will contain counts of study participants, percentages of study participants in parentheses and the number of events where applicable. A study participant who has multiple events in the same SOC and PT will be counted only once in the study participant counts but all events will be included.

In summaries including relationship, the following relationships will be summarized: 'Not related', 'Related'. Study participants who experience the same event multiple times will be included in the most related category for tabulations by maximum relationship. Events with missing relationship will be considered as 'Related' but recorded as missing in the listings.

In summaries including intensity, the following intensity categories will be summarized: 'Mild', 'Moderate', 'Severe'. Study participants who experience the same event multiple times will be included in the most severe category for tabulations by maximum intensity. Events with missing intensity will be considered as 'Severe' events for summary purposes but recorded as missing in the listings.

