**13 APPENDICES**

Treatment	Sequence	Treatment	Overall
Study participant disposition	X		
Protocol deviations	X		
Demographics	X		
Medical history	X		
Lifestyle	X		
Prior medications	X		
Concomitant medications		X	X
Adverse Events		X	X
Laboratory tests	X		
Other safety continuous measurements (vital signs, ECG)	X		
Safety categorical results (laboratory shift tables, PDILI)	X		
PK plasma for PSL and its metabolites		X	
PK for EE and LN		X	

REDACTED COPY  
 This document cannot be used to support any marketing authorization application and any extensions or variations thereof.

---

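### The adverse event tables do not clearly specify how many participants had a TEAE on PSL, and the PSL+OC window ends at different times after PSL in the two sequences

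*SAP*

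**What the plan says.** SAP Table 2-1 gives the secondary objective as "To evaluate the safety and tolerability of PSL in healthy female study participants", with the endpoint "Incidence of TEAEs and SAEs".

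SAP 3.6 fixes the layout: "Concomitant medication and adverse event tables will be presented separately for each study part by treatment (OC alone, PSL alone, and OC+PSL"). The table in SAP 13 marks the row "Adverse Events" under Treatment and under Overall. No column for PSL with or without OC is named.

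SAP 10.2 assigns each event to a column by onset. For Part 1 Sequence A, "all AEs starting after OC intake on Day 13 through Day 34 (prior to OC intake) will be attributed to PSL+OC". For Part 1 Sequence B the PSL+OC window opens at the OC tablet on Day 30 and closes on Day 43; from Day 44 events go to the Safety Follow-up (SFU) column. The general rule is that onsets more than 168 hours after the last dose of study medication belong to SFU.

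SAP 10.2 also says: "The number and percentage of study participants who experience TEAEs will be summarized by MedDRA SOC, PT, treatment sequence and treatment period". SAP 2.2 recognises two treatment periods, PSL+OC and OC alone. SAP 6.4 speaks of a third.

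Protocol 9.4 sets the three treatment groups and also asks for AE incidence according to intake of PSL. SAP 3.9 replaces the latter: "As the relationship to PSL alone is not documented in the CRF, the relationship to study medication (PSL, PSL+OC, and OC) will be analyzed".

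**The concern.** The objective is about PSL, but the tables divide each PSL course at a single OC tablet and give no total across the two pieces. Since the CRF does not record relationship to PSL separately, the onset window is the only tabulated means of isolating PSL.

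The two pieces also differ in dose phase. PSL alone holds the up-titration and most of the days at the top dose. PSL+OC holds the last two top-dose days, the taper, and a stretch with no PSL at all. Protocol 2.3 says "The AEs tend to be dose related in frequency and intensity, self-limiting, and tend to decrease in intensity over the first few days of dosing", so phase matters to how the columns are read. The off-PSL stretch also differs in length between sequences, so the pooled PSL+OC column mixes two definitions.

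At stake is whether a reader of the tables can answer a simple question: of those given PSL, how many had a TEAE while on it or shortly after?

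**Working it through.** **Inputs.** The Part 1 dosing days come from SAP Table 2-2 and SAP 3.2.2, and the AE windows from SAP 10.2. The OC day is counted in PSL+OC.

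**1. The plan's own figure.** SAP 3.2.2 states 19 days of PSL in Part 1. Sequence A, Days 1 to 19: 19 − 1 + 1 = 19. Sequence B, Days 18 to 36: 36 − 18 + 1 = 19. Both agree.

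**2. Content of the two PSL columns, Part 1.**

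| | Sequence A | Sequence B |
|---|---|---|
| PSL alone | Days 1–12: 12 days | Days 18–29: 12 days |
| PSL+OC, 400mg BID | Days 13–14: 2 | Days 30–31: 2 |
| PSL+OC, taper | Days 15–19: 5 | Days 32–36: 5 |
| PSL+OC, off PSL | Days 20–33: 14 | Days 37–43: 7 |
| PSL+OC total | 21 days | 14 days |
| Share off PSL | 14/21 = 67% | 7/14 = 50% |

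Of the 19 PSL days, 12 fall in PSL alone and 2 + 5 = 7 in PSL+OC. Sequence A runs on to the second OC dose on Day 34, so it takes in the whole washout. Sequence B stops 7 days after the last PSL dose. The Sequence B washout goes to OC alone.

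**3. Same interval since PSL, different column.** Take an onset 9 days after the last PSL dose. In Sequence A this is Day 19 + 9 = Day 28, which goes to PSL+OC. In Sequence B it is Day 36 + 9 = Day 45, which goes to SFU.

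**4. Can the PSL count be recovered from the columns?** If x participants have a TEAE under PSL alone and y under PSL+OC, out of n, the number with either lies between max(x, y) and min(n, x + y). Illustration with assumed counts and n = 14, the number of Part 1 completers:

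- x = 7, y = 5: between 7 and 12 of 14 (50% to 86%).
- x = 8, y = 6: between 8 and 14 of 14 (57% to 100%).

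The AE tables use the Safety Set, whose size is not stated, so these figures only show the width of the gap. Overall can cap the count but does not give it. SAP 10.2 defines a TEAE from the first dose of OC or PSL, so in Sequence B Overall includes events from Day 1 up to the first PSL dose on Day 18.

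**5. The possible exception.** With the SAP 2.2 meaning, which the AE listings in SAP 10.2 also use, the summary by treatment period would count each participant once over the whole PSL period, within sequence. With the SAP 6.4 meaning it would reproduce the three-way split. The onset windows and the sorting by a PSL+OC column in SAP 10.2 follow the three-way layout. The text does not settle which is meant.

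**6. Effect of one cutoff.** Ending PSL+OC 168 hours after the last PSL dose puts the end at about Day 26 in Sequence A (19 + 7) and leaves Day 43 in Sequence B (36 + 7). Each window is then 2 + 5 + 7 = 14 days, and PSL alone plus PSL+OC is 12 + 14 = 26 days in both sequences.

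**The case against.** The case for leaving the plan alone has several sound parts.

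- *The endpoint is tabulated.* SAP 10.2 plans an overview with any TEAE, any serious AE, and severe, related and discontinuation TEAEs, by treatment with an Overall column. PSL alone is itself an incidence on PSL over 12 of the 19 days. A reader might infer that the secondary endpoint is not estimated; the documents do not support that. What is missing is one clearly specified participant-level count for PSL.
- *A table may already do it.* On the two-period reading, the SAP 10.2 summary would. This stands as a possibility, so a flat statement that no table counts TEAEs on PSL goes too far. Even then, no cutoff after PSL is stated.
- *The listings suffice.* They carry participant, onset date and time, and dosing times, so the count and the dose at onset could be worked out by hand. True, but a secondary objective should not depend on that.
- *The split is the protocol's.* Protocol 9.4 sets the same three groups. This justifies keeping the sub-columns; it is no reason to omit their total.
- *No comparison is planned.* The AE outputs are descriptive. A reader might take PSL alone against PSL+OC as the effect of adding OC, but the SAP does not propose it. A footnote is enough.
- *Little is left to report.* SAP 1 says that no one will enter Part 2 and that only a subset of outputs will be produced. This limits the point to Part 1.

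**Conclusion.** The concern holds as a gap in the table specification. The SAP clearly specifies no count of participants with a TEAE on PSL; the two PSL columns overlap in participants, and their union cannot be derived from the table totals. The PSL+OC window is also inconsistent: 21 days with 14 off PSL in Part 1 Sequence A, against 14 days with 7 off PSL in Sequence B. Onsets at the same interval since the last PSL dose can therefore land in different columns.

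The day counts follow from the documents and assume dosing on the scheduled days. The ranges in the illustration rest on assumed event counts and on n = 14. The practical weight is modest: the data are collected, the listings are planned, and only Part 1 will be reported.

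**What to change.** In SAP 3.6, 10.2 and 13:

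1. Add an Any PSL column to the TEAE tables. Count each participant once, for onset from the first PSL dose to the last PSL dose plus the 168 hours that SAP 10.2 already uses.
2. Keep PSL alone and PSL+OC as sub-columns, and end PSL+OC at that same cutoff in both sequences. Otherwise Sequence A events after about Day 26 would sit in a sub-column but not in its parent.
3. Put later Sequence A onsets (after about Day 26 and before OC on Day 34) in a separate off-PSL or washout column.
4. Define treatment period in SAP 10.2, consistently with SAP 2.2 and 6.4.
5. Add a footnote that PSL alone and PSL+OC differ by dose phase and are not a comparison of the effect of OC.

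A table by dose phase at onset is optional.

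The cost is one or two extra columns from dates already collected, and a PSL+OC count in Sequence A that may differ from the one now planned. No new data are needed.

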### 3.7 Center pooling strategy

The data will come from one center. The statistical analyses will not be performed by center.

### 3.8 Coding dictionaries

Adverse events and medical history will be coded using version 22.0 of the Medical Dictionary for Regulatory Activities (MedDRA®). Medications will be coded according to the latest version of the World Health Organization Drug Dictionary (WHODD) (Version SEP/2017). Medical procedures will not be coded.

The versions of the coding dictionaries used will be displayed in the relevant TFLs.

### 3.9 Changes to protocol-defined analyses

- Changes in the name of analysis datasets (section 9.1 of the protocol):
  - The analysis set “Enrolled set” will be renamed as “All Study Participants” in the SAP and will correspond to all study participants who sign the informed consent form.
  - The analysis set “Pharmacokinetic Per Protocol Set (PK-PPS)” will be renamed as “Pharmacokinetic Set (PK Set)” in the SAP and will still correspond to the protocol definition of PK-PPS.
- For the purpose of the analysis of concomitant medications and adverse events 3 groups will be created, based on the treatment administered. The results will be presented for PSL alone, OC alone and the combination of PSL and OC.
- For the primary PK analysis, ping-pong plots have been added for EE and LN for  $C_{max}$ , and AUC for OC with and without PSL.
- Ping-pong plots have also been added for  $C_{max,ss}$  and  $AUC_{\tau}$ , for PSL and its two metabolites ( [REDACTED] and [REDACTED] ) for PSL with and without OC.
- Ping-pong plots have been added for  $C_{max,ss}$ ,  $AUC_{\tau}$ ,  $MR_{AUC_{\tau}}$ ,  $MR_{C_{max,ss}}$ ,  $CL_{ss}$ ,  $t_{1/2}$ , for PSL (with and without OC).
- Furthermore, the relationship between MR and  $C_{max}$  (with and without PSL) of EE and LN, and the exposure to PSL ( $AUC_{\tau}$ ) will be explored.
- Ctrough and MR based on  $AUC_{\tau}$  of PSL and its two metabolites, will also be compared between days (with OC [Day 13 for Sequence A and Day 30 for Sequence B] and without OC [Day 12 for Treatment Sequence A and Day 29 for Treatment Sequence B] using analysis of variance on the log-transformed parameters and estimation of geometric ratio of PK parameters between days with their 90% CI will be provided.
- Furthermore, the relationship between individual  $C_{max}$  (with and without PSL) of EE and LN and the exposure to PSL ( $AUC_{\tau}$ ) will be assessed by scatterplots and linear regression analyses.
- According to the protocol, the occurrence and incidence of AEs will be summarized by treatment sequence according to the intake of PSL (pretreatment or treatment-emergent) and

by intensity or relationship to PSL. As the relationship to PSL alone is not documented in the CRF, the relationship to study medication (PSL, PSL+OC, and OC) will be analyzed. Consequently, the definition of TEAE will be related to treatment (PSL, PSL+OC, or OC) and a TEAE will be attributed to a treatment according to the start date.

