8.4.1 Time period and frequency for collecting AE and SAE information

All AEs and SAEs will be collected from the signing of the ICF and at the time points specified in the Schedule of Activities.

Medical occurrences that begin before the start of study medication, but after obtaining informed consent will be recorded on the Medical History/Current Medical Conditions section of the eCRF, not the AE section.

All SAEs will be recorded and reported to the Sponsor or designee within 24 hours, as indicated in Appendix 3 (Section 10.3). The Investigator will submit any updated SAE data to the Sponsor within 24 hours of it being available.

The Investigator is specifically requested to collect and report to UCB (or its representative) any SAEs (even if the Investigator is certain that they are in no way associated with the study medication), up to 30 days from the end of the study for each study participant, and to also inform study participants of the need to inform the Investigator of any SAE within this period. Serious AEs that the Investigator thinks may be associated with the study medication must be reported to UCB regardless of the time between the event and the end of the study.

The method of recording, evaluating, and assessing causality of AE and SAE and the procedures for completing and transmitting SAE reports are provided in Appendix 3 (Section 10.3).

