## 10.2 Adverse events

All AEs will be coded using the MedDRA® and characterized as pre-treatment and treatment-emergent according to the intake of the study medications (PSL, OC).

Adverse events with a start date prior to the first dose of study medication will be defined as pre-treatment AEs. For sequence A, the first dose of PSL is given on Day 1. For sequence B, the first dose of OC is given on Day 1.

A treatment-emergent AE (TEAE) is defined as any AE with a start date/time on or after the first dose of study medication (OC or PSL) or any unresolved event already present before administration of study medication that worsens in intensity following exposure to the treatment. Where dates are missing or partially missing, AEs will be assumed to be treatment-emergent, unless there is clear evidence to suggest that the AE started prior to the first dose of study medication. Missing or partially missing dates for AEs will be handled as described in Section 4.2.4.

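### SAP 10.2 counts worsening as treatment-emergent, but TEAEs are placed by start date only, so an event that worsens on a later treatment is not counted under it

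*SAP*

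**What the plan says.** SAP 10.2 gives two routes to a TEAE. One is onset on or after the first study medication. The other is "any unresolved event already present before administration of study medication that worsens in intensity following exposure to the treatment". The same section also states, without exception, "Adverse events with a start date prior to the first dose of study medication will be defined as pre-treatment AEs".

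Attribution has one route only. SAP 3.9 says that "a TEAE will be attributed to a treatment according to the start date", and SAP 10.2 repeats it: "Adverse events will be attributed to the treatment (OC, PSL or OC+PSL) after which they start". In Part 1 the first window for Sequence A is "all AEs starting after the first intake of PSL through Day 13 (prior to OC intake) will be attributed to PSL", and for Sequence B "all AEs starting after the OC intake on Day 1 through Day 18 (prior to PSL intake) will be attributed to OC". No sentence says which treatment receives a worsening.

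The documents also differ on recording. Under Protocol 8.4.1, occurrences after consent but before study medication "will be recorded on the Medical History/Current Medical Conditions section of the eCRF, not the AE section". SAP 10.2 says "All AEs will be recorded in the CRF from the time of informed consent until study completion or termination". Protocol Appendix 3 (10.3.1) counts exacerbation of a pre-existing condition as an AE, and 10.3.3 puts new information into the existing eCRF record.

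**The concern.** The TEAE definition recognises worsening and the attribution rule does not. An event can therefore be treatment-emergent because of what happened on a treatment and still not be tabulated under that treatment.

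This matters because PSL safety and tolerability is a secondary objective, with TEAE and SAE incidence as its endpoint. SAP 10.2 also plans tables by maximum intensity. Protocol 2.3 describes PSL events as dose related in both frequency and intensity, and reports two participants in this study with transiently severe psychiatric events. How worsening is assigned to a treatment is therefore part of what the safety tables are meant to show.

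**Working it through.** The plan gives no figure to reproduce. The check runs example events through the Part 1 windows of SAP 10.2.

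**Inputs (SAP 10.2, Part 1)**
- Sequence A: PSL from first intake on Day 1 to OC on Day 13; PSL+OC from then to OC on Day 34; OC alone from then to Day 41.
- Sequence B: OC alone from OC on Day 1 to PSL on Day 18; PSL from then to OC on Day 30; PSL+OC from then to Day 43.

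**Placement of each event under the written rule, and by date of worsening**

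| Event | TEAE because of | By start date (SAP) | By date of worsening |
|---|---|---|---|
| A, pre-dose, worsens Day 8 | worsening | none | PSL |
| B, pre-dose, worsens Day 2 | worsening | none | OC alone |
| B, pre-dose, worsens Day 25 | worsening | none | PSL |
| B, starts Day 2, worsens Day 20 | onset | OC alone | PSL |
| B, starts Day 16, worsens Day 26 | onset | OC alone | PSL |
| A, starts Day 5, worsens Day 14 | onset | PSL | PSL+OC |
| A, starts Day 25 (washout), worsens Day 35 | onset | PSL+OC | OC alone |

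**Reading the table**
1. Rows 1 to 3: the event is a TEAE and, by its start date, also pre-treatment. No window contains that date. The table in SAP Section 13 gives adverse events an Overall column, so the event may be counted there and under no treatment.
2. Rows 4 and 5: the event is a TEAE by onset and belongs in the OC-alone column. What is lost is the worsening under PSL.
3. Rows 6 and 7: the same gap exists in Sequence A. In row 7 it is OC alone that loses the worsening, the opposite direction to rows 4 and 5.

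**Size per participant**
- With the 14 Part 1 completers (7 per sequence) at risk: 1/14 = 7.1%. Within Sequence B alone: 1/7 = 14.3%.
- SAP 10.2 has a table of non-serious TEAEs above 5%. Since 1/20 = 5.0% and 1/19 = 5.3%, one participant takes a term above 5% whenever 19 or fewer are at risk.
- The documents do not give the number of affected events. A missed worsening lowers a later column's incidence only if that woman has no other event counted in the same row.

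**The case against.** The strongest reply is that the recording rules may already give a worsened pre-dose event a column. Protocol 8.4.1 sends it to Medical History, and Appendix 3 makes its exacerbation an AE. If that AE carries the date of worsening as its start date, start-date attribution works. This is a fair reading, but neither document states that convention. Entering updates in the existing record (10.3.3) points the other way for an event already on the AE page, and SAP 10.2 still expects pre-treatment AEs in the data.

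A second reply is that the worsening clause can be read per treatment: it does not contain the word first, and SAP 3.9 ties the TEAE definition to treatment. That reading widens the definition, but placement is still by start date.

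A third reply is that the effect is small. An event in rows 4 and 5 must still be ongoing on Day 18, after one OC dose on Day 1 and a 14-day washout, in healthy women whose eligibility is checked again that day. The summaries are descriptive, only a subset of Part 1 outputs will be reported (SAP Section 1), and the AE listings carry dates, pattern and intensity. This stands as a limit on size. It does not supply the missing rule.

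A reader might infer more: that the rule inflates OC alone in both incidence and severity and systematically flatters PSL. The documents do not support that.
- **Incidence:** events that start after OC and before PSL are properly OC-alone events.
- **Severity:** a grade reached on PSL would show under OC alone only if one record is overwritten with its worst grade. The documents do not settle this, and the maximum-intensity rule in SAP 10.2 speaks of repeated events, not one event that changes grade.
- **Direction:** the Sequence A washout case works the other way.

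**Conclusion.** The point holds as a gap between definition and attribution. Followed literally, the SAP leaves a worsened pre-dose TEAE without a treatment column in either sequence, and never counts a worsening under a later treatment when the event began in an earlier window. In Sequence B this can understate PSL; in Sequence A it can understate OC alone or PSL+OC. The net direction is not certain.

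One affected participant is about 7% if 14 are at risk. That figure uses completers; the Safety Set includes everyone dosed at least once, so the percentage would be lower if more women were dosed. Few cases are expected and no count is available. The conclusion assumes that a worsening keeps the start date of the event. If the site opened a new record dated at each worsening, most of the problem disappears, but the plan would need to say so.

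**What to change.** In SAP 3.9 and 10.2:
- Treat an increase in intensity after the first dose of a treatment, including in a pre-dose event, as a TEAE of that treatment, dated at the worsening.
- Keep an event that began in an earlier window in its onset column, at the intensity it had before that dose.
- Tabulate each intensity in the window where it occurred.
- State whether a change of intensity opens a new AE record or updates the existing one.
- Reconcile the pre-treatment AE category, and AE recording from consent, with Protocol 8.4.1 (Medical History) and Appendix 3 (exacerbation is an AE). Part 1 dosing is complete and Part 2 will not enrol, so the practical route is for the SAP to describe how Part 1 events were actually recorded.

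The cost is a few sentences and a small derivation. If dates of intensity change were not captured in Part 1, list the affected events individually and footnote the AE tables.
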